5.7 Study Drug Discontinuation Criteria

Subjects **must** be permanently discontinued from BOTH study drugs (INCMGA00012 and INCAGN01876) if any one or more of the following occurs:

- Grade 2 or higher toxicity [per NCI CTCAE v 5.0] that is at least possibly related to one of the study drugs AND does not improve with optimal medical management to grade 1 or less within 12 weeks from last dose of study drugs or results in subject being unable to taper off corticosteroids (or, if on corticosteroids prior to the toxicity, unable to taper down to subject's baseline/pre-toxicity dose) within 12 weeks from last dose of study drugs, with the following exceptions:
 - Grade 2 Nervous System toxicity (e.g., leg weakness, aphasia, etc) that is *due to* intratumoral/peritumoral enlargement (contrast-enhancing or T2/FLAIR) or intratumoral/peritumoral cerebral edema
 - Grade 3-4 Nervous System toxicity (e.g., leg weakness, aphasia, etc) that is *due to* intratumoral/peritumoral enlargement (contrast-enhancing or T2/FLAIR) or intratumoral/peritumoral cerebral edema AND improves to grade 2 or less within 7 days of optimal medical management
 - Grade 3 Cerebral Edema
 - Grade 4 Cerebral edema that improves to grade 3 within 7 days of optimal medical management

- Any grade endocrinopathy that is controlled by hormone replacement
- Grade 4 irAE, as defined in [Section 9.1.2, *Immune-Related Adverse Events*](#), with the following exception:
 - Grade 4 endocrinopathy that is controlled by hormone replacement
- Grade 3 hepatitis, pneumonitis, nephritis, myocarditis, pericarditis, encephalitis, myasthenia gravis, posterior- or pan-uveitis, episcleritis, peripheral neuropathy (including Guillain-Barre syndrome), autoimmune hemolytic anemia, acquired hemophilia, or autonomic neuropathy
- Recurrent Grade 2 pneumonitis
- Any grade transverse myelitis
- The subject becomes pregnant.
- Consent is withdrawn by the subject.
 - Note:** Consent withdrawn means that the subject can no longer be followed and no additional data can be collected. Subjects may choose to discontinue study treatment and remain in the study to be followed for progression and survival.
- Further participation would be injurious to the subject's health or well-being, in the investigator's medical judgment.
- Confirmed radiographic progression of disease per modified RANO criteria (as defined in [Section 7](#)).
 - Exception: If subject meets radiographic criteria for PD but then undergoes a surgical resection of the area of radiographic PD per their treating oncologist's recommendation, the patient may stay on study and resume study drugs postoperatively if (i) histopathology from this surgery demonstrates only therapy-related changes and no viable tumor (scattered/rare atypical glial cells only would not count as viable tumor) AND (ii) there are no other, separate sites of PD on the immediate post-operative MRI.
 - Exception: If radiologic imaging *within the first 6 months* from the first dose of immunotherapy shows confirmed PD by mRANO criteria, participants not experiencing significant clinical decline may be allowed to continue study treatment for up to 3 months from the time of the scan showing confirmed PD. It is at the discretion of the treating physician whether to continue a participant on study treatment for up to 3 months pending confirmation of PD on follow-up imaging. This clinical judgment decision should be based on the participant's overall clinical condition, including performance status, clinical symptoms, and laboratory data. Subjects may receive study treatment while waiting for confirmation of PD if they are not experiencing significant clinical decline and if:
 - the subject is believed to demonstrate clinical benefit from the study regimen as determined by the treating physician;
 - the subject is adequately tolerating study therapy
- The study is terminated by the Sponsor.
- The IRB withdraws approval for the study

- Any progression or recurrence of any malignancy, or any occurrence of another malignancy that requires active treatment
- Occurrence of any AE that is related to either study drug that, in the judgment of the Investigator and/or Medical Director, compromises the subject's ability to continue study-specific procedures or is considered to not be in the subject's best interest.

A subject **may** be permanently discontinued from BOTH study drugs (INCMGA00012 and INCAGN01876) as follows:

- If, during the course of the study, a subject is found not to have met eligibility criteria, the medical monitor, in collaboration with the investigator, will determine whether the subject should be withdrawn from the study.
- If a subject is noncompliant with study procedures or study treatment in the investigator's opinion, the sponsor should be consulted for instruction on handling the subject.

A subject **must** be permanently discontinued from ONE study drug (either INCMGA00012 OR INCAGN01876) and **may continue** the other study drug if any of the following occurs:

- The subject has a grade 3 or higher infusion reaction that is clearly linked to only **one** of the study drugs. The temporal relationship between study drug administration and the reaction must be such that no other reasonable explanation exists for the subject's reaction beyond that specific study drug. If a subject has a grade 3 or higher infusion reaction and it is unclear which study drug was responsible, both study drugs must be permanently discontinued.

Reasons and procedures for replacing subjects are detailed in [Section 3.2 Replacement of Subjects](#).

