3 INVESTIGATIONAL PLAN

3.1. General Design

This is a single-center, phase II, open label study evaluating the efficacy and safety of the combination of INCMGA00012, INCAGN01876 and SRS for patients with recurrent GBM.

The overall study population will be broken down into two cohorts: Cohort A (N=16) and Cohort B (N=16). Subjects for whom surgical resection is not clinically indicated at the time of study

screening will be enrolled into Cohort A (non-surgical cohort). Subjects for whom surgical resection is clinically indicated at the time of study screening will be enrolled into Cohort B (surgical cohort).

The first 6 subjects enrolled onto the study must be enrolled onto Cohort A and will be enrolled in two groups of 3 subjects (i.e., a “3+3” design) as part of a safety run-in period. After enrollment of the first 3 subjects, enrollment is put on hold until all of the first 3 subjects have completed the safety monitoring period (completion of SRS and one cycle of INCMGA00012 and INCAGN01876). If only 0-1 of the first 3 subjects experiences a criterion for study drug discontinuation, as defined in [Section 5.7, Study Drug Discontinuation Criteria](#), then the next 3 subjects will be enrolled. If 2 of the first 3 subjects experience a criterion for study drug discontinuation, the study will be paused for reconsideration of the dosing and schedule of investigational agents.

Of the first 6 subjects enrolled during the safety run-in, if 3 or greater subjects experience a criterion for study drug discontinuation, then the study will be paused for reconsideration of the dosing and schedule of investigational agents. If only 0-2 of the first 6 subjects enrolled during the safety run-in experience a criterion for study drug discontinuation, then enrollment to both cohorts A and B will commence uninterrupted.

If at any point during the safety run-in a stopping rule is met and the dose/schedule of investigational agents is changed, the safety run-in will start over again with another 6 patients. If Cohort A has reached enrollment of 12 subjects and the criteria to move beyond the safety run-in phase has still not yet been met (i.e., at least 6 patients have been treated at the same dose/schedule and only 2 or fewer have experienced a criterion for study drug discontinuation), the trial (including Cohort B) will be terminated due to intolerability of the study regimen.

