3.1.3. Follow Up Phase

Any subject who permanently discontinues the study drugs based on any reason outlined in [Section 5.7](#) will proceed to follow-up.

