3.3. Duration of Individual Subject Study Participation

After signing the ICF, screening procedures commence. Each enrolled subject begins study treatment. Treatment continues until the subject meets any one or more of the criteria for study drug discontinuation (see [Section 5.7; Study Drug Discontinuation Criteria](#)). When a subject discontinues study drug but has not withdrawn consent, the subject enters the follow-up period. Subjects are taken off study if any of the following criteria apply:

- Lost to follow-up
- Withdrawal of consent
- Death
- Sponsor decides to terminate the study

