5.8.3. Management of cerebral edema

Due to the immunologic nature of anti-PD-1 and GITR therapy, cerebral edema could theoretically result as a consequence of immune infiltration of the brain. In addition, SRS is expected to elicit cerebral edema. Symptoms related to cerebral edema may include headache or neurologic deficit that is either new or worsened. Participants with any signs or symptoms of cerebral edema in the investigator's judgment should be treated as clinically appropriate including initiation or increased dosing of systemic corticosteroids, osmotic diuretics, and/or surgical decompression. Subsequent study drug treatment should be immediately interrupted if significant clinical symptoms attributable to cerebral edema in the investigator's judgment develop. Treatment with additional study drug may only be re-initiated if clinically significant symptoms attributable to cerebral edema have stabilized or significantly resolved in the investigator's judgment.

Participants who develop grade 4 cerebral edema (CTCAE v5) attributable to study drug administration should not receive further study drug. Grade 4 cerebral edema is defined as life-threatening or requiring urgent intervention. For this study, urgent intervention refers to urgent/emergent intensive care unit admission, intubation for hyperventilation, administration of hypertonic or hyperosmotic agents, and/or urgent/emergent surgical decompression.

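### Drug-attributed grade 4 cerebral edema ends treatment under Section 5.8.3 but is missing from the Section 5.7 list that the safety run-in counts

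*Combined protocol and SAP*

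**What the plan says.** Section 5.7 lists the events that require permanent discontinuation of both drugs. The first is "Grade 2 or higher toxicity [per NCI CTCAE v 5.0] that is at least possibly related to one of the study drugs", if it has not improved to grade 1 or less, or steroids cannot be tapered, within 12 weeks of the last dose. Among its exceptions are grade 3 cerebral edema and "Grade 4 Cerebral edema that improves to grade 3 within 7 days of optimal medical management". Another covers grade 3-4 nervous-system toxicity due to tumor enlargement or edema that improves to grade 2 or less within 7 days.

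Section 5.8.3 deals with cerebral edema specifically: "Participants who develop grade 4 cerebral edema (CTCAE v5) attributable to study drug administration should not receive further study drug". It has no exception for improvement.

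The run-in rule in Section 3.1 is tied to Section 5.7. "If only 0-1 of the first 3 subjects experiences a criterion for study drug discontinuation, as defined in" Section 5.7, the next three are enrolled; 2 of 3 means a pause. "If only 0-2 of the first 6 subjects enrolled during the safety run-in experience a criterion for study drug discontinuation", both cohorts enroll; 3 or more means a pause. Section 3.3 says, again pointing to 5.7: "Treatment continues until the subject meets any one or more of the criteria for study drug discontinuation". Neither section mentions 5.8.3.

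**The concern.** One event gets two answers. Take a subject whose grade 4 cerebral edema is attributed to study drug and falls to grade 3 by day 5. Under 5.8.3 the subject should not be dosed again. Under the first 5.7 criterion the event is exempt.

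Two things are at stake. The first is clarity about re-exposure after a life-threatening event. Sections 5.5 and 5.8.1 allow no dose reduction, so any resumption is at full dose. The second is the run-in, which opens both cohorts on a count of 5.7 criteria. Section 12.1 names cerebral edema as the likeliest cause of a drug-related serious event, so the omission affects the toxicity that the run-in most needs to detect.

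**Working it through.** The plan states no figure on this point, so there is none to reproduce. The check is a comparison of the sections, followed by the arithmetic of the counting rule.

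**Step 1: does any other 5.7 criterion catch the event?** Assume edema in or around the tumor, grade 4, attributed to study drug, grade 3 within 7 days.

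- First criterion (related toxicity persisting 12 weeks): exempt. If the edema stays at grade 3, the separate grade 3 exception applies.
- Grade 4 immune-related event: does not apply. Section 9.1.2 says such edema is not an immune-related event even when attributed to drug. Edema elsewhere is not excluded by that sentence and might qualify.
- Listed grade 3 organ toxicities: cerebral edema is not among them.
- Continued participation injurious to health, or a related event judged not to be in the subject's best interest: can apply, but only by case-by-case judgment.

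So only a judgment criterion brings the 5.8.3 stop into the count.

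**Step 2: effect on the count.** Limits from Section 3.1; *other* means subjects counted under another 5.7 criterion.

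| Stage | Other | Edema stop | Recorded if edema is not counted | Recorded if counted |
|---|---|---|---|---|
| First 3 | 1 | 1 | 1 of 3: enroll next 3 | 2 of 3: pause |
| All 6 | 2 | 1 | 2 of 6: both cohorts open | 3 of 6: pause |

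This needs no assumed rate.

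**Step 3: illustration only.** Take 3 of 3 as a pause too (3.1 names only 2 of 3), subjects as independent, and edema stops as separate from other counted events. With X the number of events in three subjects, each with event probability p,

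P(pass) = P(X=0)·P(X≤2) + P(X=1)·P(X≤1).

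- p = 0.10: 0.729 × 0.999 + 0.243 × 0.972 = 0.9645
- p = 0.15: 0.9174
- p = 0.20: 0.512 × 0.992 + 0.384 × 0.896 = 0.8520
- p = 0.25: 0.7712
- p = 0.30: 0.343 × 0.973 + 0.441 × 0.784 = 0.6795

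Suppose other events occur in 10% to 20% of subjects and the edema event in a further 5% to 10%. Both ranges are assumptions. If the judgment criteria capture no edema events, P(pass) is too high by 0.9645 − 0.9174 = 4.7 points at the low end and 0.8520 − 0.6795 = 17.2 points at the high end. If they capture half, the gap is 0.9434 (p = 0.125) − 0.9174 = 2.6 points to 0.7712 − 0.6795 = 9.2 points. At 90% capture it is 0.9230 (p = 0.145) − 0.9174 = 0.6 points to 0.6985 (p = 0.29) − 0.6795 = 1.9 points. The zero-capture figures are upper bounds for the assumed rates.

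**The case against.** The strongest reply is that the exception in 5.7 only takes an event out of one criterion. It does not permit dosing. An investigator who follows 5.8.3 breaches nothing in 5.7, and 5.8.3 can be read as the specific and stricter rule. Section 5.7 is also not the only source of stops: Section 3.1.2 ends treatment for unacceptable adverse events, and Section 5.8.3 requires interruption for significant edema symptoms. An investigator who stops drug for a life-threatening related event would often be applying one of the judgment criteria, and the event would then count. Much of this stands. A reader might infer that the protocol authorizes re-dosing against 5.8.3; it does not. But 3.1 counts criteria, not stops. Whether a judgment criterion was met is left to the investigator, who may take the explicit exemption as a reason not to invoke one.

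A second reply is that the two thresholds may be deliberate. Section 5.8.3 itself expects radiosurgery to cause edema, so sparing improving edema that is only possibly drug-related, while stopping for edema attributable to drug, is coherent. That is a fair reason to leave the attribution level to the team. It does not help with edema clearly attributed to drug, which falls under both rules. Carrying the 7-day recovery exception into 5.8.3 would also remove the conflict, but by weakening the safety stop.

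A reader might also infer from Section 3.1.3 that a subject stopped under 5.8.3 never enters follow-up, since that section names only 5.7 reasons. Section 3.3 answers this: anyone who discontinues drug without withdrawing consent enters follow-up.

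**Conclusion.** The plan is wrong as written, in a limited way. A permanent stop in 5.8.3 for drug-attributed grade 4 cerebral edema is missing from 5.7, and both the run-in count in 3.1 and the continuation rule in 3.3 refer to 5.7. For edema in or around the tumor that improves to grade 3 within 7 days, counting depends on discretion. One uncounted event is enough to reverse either run-in decision.

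That is the size that can be stated. The documents give no rate for drug-attributable grade 4 edema under this combination, so a reader should not infer that the chance of passing the run-in is inflated by any particular amount. The range in the working is illustrative and shrinks as the judgment criteria capture more events.

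The conclusion rests on the event being attributed to study drug in the sense of 5.8.3, which the plan does not define. It does not extend to the 12-week clause outlasting the first-3 decision, or to the observation window for subjects 4 to 6. Those are design choices, partly covered by the same judgment criteria, and are not shown to be errors.

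**What to change.** (a) Add a stand-alone must-stop criterion to 5.7: grade 4 cerebral edema attributable to study drug (see 5.8.3), whether or not it improves. Deleting the exception alone is not enough, because the first criterion would still require 12 weeks without recovery or steroid taper.

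(b) Limit the grade 4 edema exception in 5.7 to events not attributed to study drug under 5.8.3. Apply the same limit to the grade 4 part of the nervous-system exception when the cause is cerebral edema, so that the event does not stay exempt under another term. State which level of the five-level relatedness scale in Section 9.2 counts as attributable. At least possibly related matches 5.7 but would take drug from some subjects whose edema is mainly due to radiosurgery. Probably or definitely related avoids most of that. The choice is the team's.

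(c) State in 3.1 that this event counts as a run-in event.

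The cost is wording in three sections. The sample size and the response-rate test do not change. The run-in may pause somewhat more often, and a pause that changes the dose or schedule restarts it with six more subjects under 3.1.

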5.8 Management of Study Drug Toxicities

5.8.1. Supportive care for Immune-Related Adverse Events (irAEs)

GITR represents an important immune control receptor. It is anticipated that combining GITR agonism PD-1 inhibition could cause more frequent, more severe, and/or new immune-related toxicities compared to the well-described immune-related toxicity for single agent PD-1 inhibition ([Brahmer et al, J Clin Oncol 2018](#)). For this reason, a variety of measures are included to mitigate these potential risks. These measures are consistent with published guidelines for immune-related AEs associated with anti-PD-1 drugs, but are meant to apply to any suspected immune-related AEs from other immuno-oncology agents such as the combination of INCMGA00012 and INCAGN01876

Immune-related AEs may be defined as an AE of unknown etiology, associated with drug exposure and consistent with an immune phenomenon. Immune-related AEs may be predicted based on the nature of the INMGA0012 and INCAGN01876 compounds, their mechanism of action, and the extensive reported experience with immunotherapies that have a similar mechanism of action. Special attention should be paid to AEs that may be suggestive of potential irAEs. An irAE can occur shortly after the first dose or several months after the last dose of treatment.

If an irAE is suspected, efforts should be made to rule out neoplastic, infectious, metabolic, toxin or other etiologic causes before labeling an AE as an irAE. Subjects who develop a \geq Grade 2 irAE should be discussed immediately with the principal investigator.

Recommendations for management of *specific* immune-mediated AEs such as pneumonitis, enterocolitis, hepatitis, dermatitis, neuropathies, endocrinopathies, and other immune-mediated AEs, and are based on recently published guidelines for the management of immunotherapy-related toxicities that have recently been published by the National Comprehensive Cancer Network (NCCN) in partnership with the American Society of Clinical Oncology (ASCO), available here:

https://www.nccn.org/professionals/physician_gls/pdf/immunotherapy.pdf

and here:

<http://ascopubs.org/doi/10.1200/JCO.2017.77.6385>

and described in detail in **Appendix 1** with specific application to this protocol. These recommendations include management of the toxicity itself, as well as guidance for dose interruptions/delays of the investigational agents. There are no dose reductions or dose escalations permitted for either investigational agent.

5.8.2. Management of infusion-related reactions

Emergency equipment and medication for the treatment of potential adverse effects (e.g. antihistamines, bronchodilators, IV saline, corticosteroids, acetaminophen, and or epinephrine) secondary to infusion of INCMGA00012 and INCAGN01876 must be available for immediate use.

Acute infusion reactions are defined as any AE that occurs during the infusion or within 2 hours after the infusion is completed. Emergency equipment and medication for the treatment of these potential adverse effects (eg, antihistamines, bronchodilators, IV saline, corticosteroids, acetaminophen, and/or epinephrine) must be available for immediate use.

Acute infusion reactions can include cytokine release syndrome, angioedema, or anaphylaxis, and differ from allergic/hypersensitive reactions, although some of the manifestations are common to both AEs. Signs and symptoms usually develop during or shortly after drug infusion and generally resolve during the infusion or within one day after the infusion.

Signs/symptoms may include: allergic reaction/hypersensitivity (including drug fever); arthralgia (joint pain); bronchospasm; cough; dizziness; dyspnea (shortness of breath); fatigue (asthenia, lethargy, malaise); headache; hypertension; hypotension; myalgia (muscle pain); nausea; pruritus/itching; rash/desquamation; rigors/chills; sweating (diaphoresis); tachycardia; tumor pain (onset or exacerbation of tumor pain due to treatment); urticaria (hives, welts, wheals); and vomiting. The infusion should be interrupted if any of the following AEs are observed:

- Cough
- Rigors/chills
- Rash, pruritus (itching)
- Urticaria (hives, welts, wheals)
- Diaphoresis (sweating)
- Hypotension
- Dyspnea (shortness of breath)
- Vomiting
- Flushing

The reaction(s) should be treated symptomatically, and the infusion may be restarted at

50% of the original rate.

If Investigators feel there is a medical need for treatment or discontinuation of the infusion other than described above, they should use clinical judgment to provide the appropriate response according to typical clinical practice.

The infusion should be terminated and NOT restarted if any of the following AEs occur:

- Anaphylaxis
- Laryngeal/pharyngeal edema or severe bronchospasm
- Chest pain
- Seizure

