1.3.2.3. Potential Risks of INCAGN01876

Preclinical assessments used to evaluate theoretical safety concerns with INCAGN01876 eliciting adverse proinflammatory infusion reactions did not induce cytokines that in vivo would be predictive of cytokine release syndrome in participants, so the risk of significant infusion reactions is considered to be low. For participants who have an infusion reaction associated with administration of INCAGN01876, signs and symptoms would usually develop during or shortly

after drug infusion and generally resolve completely within 24 hours of completion of infusion. Specific infusion reaction treatment guidelines are provided in **Section 5.8.2**.

INCAGN01876 is an immune modulator, and although no toxicities were identified in preclinical models, it is possible that immune related adverse events (irAEs; both nonserious and serious), similar to those described with approved immunotherapies, may occur. Adverse events of a potential immunologic etiology or irAEs may be defined as an AE consistent with an immune phenomenon associated with drug exposure after all other etiologies have been eliminated. Immune-related AEs may be expected based on the nature of INCAGN01876, its mechanism of action, and based on reported experience with other immunotherapies. Special attention should be paid to AEs that may be suggestive of potential irAEs. An irAE can occur shortly after the first dose or several months after the last dose of treatment. Suspected irAEs should be discussed with the medical monitor when possible. Guidance for management of specific irAEs is provided in **Section 5.8.1**.

Complete, detailed nonclinical and clinical data for INCAGN01876 is available in the Investigator's Brochure.

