5.5 Study drug Administration

5.5.1 Administration of INCMGA00012

INCMGA00012 is administered as an IV infusion over 60 minutes for the first infusion. If well tolerated, it may be administered over 30 minutes for subsequent treatments. On days when both study drugs are due to be administered, INCMGA00012 study product is administered first prior to administration of INCAGN01876. The only dose of INCMGA00012 used for this study is 500mg. There is no dose escalation or reduction. A 1-hour observation period is recommended after the INCMGA00012 infusion prior to beginning the INCAGN01876 infusion.

Infusion-related reactions (including anaphylaxis or cytokine release syndrome) may be associated with the administration of therapeutic antibodies. Of 199 prior study participants who have received infusions of INCMGA00012 in Study INCMGA 0012-101, 5 participants have experienced 1 infusion-related reaction each (see IB). This does not exceed the expected incidence of IRRs for the PD-1 inhibitor class. Infusion-related reactions were observed in Study INCMGA 0012-101 regardless of whether prophylaxis was administered; therefore, routine prophylaxis is not recommended. Secondary prophylaxis is recommended for participants who have experienced IRRs to INCMGA00012. Participants who experience life-threatening infusion reactions should not be retreated with INCMGA00012. Infusions reactions should be managed according to the guidelines in [Section 5.8.2](#).

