5.5.2 Administration of INCAGN01876

INCAGN01876 is administered as an IV infusion over 60 minutes for the first infusion. If well tolerated, it may be administered over 30 minutes for subsequent treatments. On days when both study drugs are due to be administered, INCMGA00012 study product is administered first prior to administration of INCAGN01876. The only dose of INCAGN01876 used for this study is 300mg. There is no dose escalation or reduction. A 1-hour observation period is recommended after the INCMGA00012 infusion prior to beginning the INCAGN01876 infusion.

Preclinical assessments used to evaluate theoretical safety concerns with INCAGN01876 eliciting adverse proinflammatory infusion reactions did not induce cytokines that in vivo would be predictive of CRS in participants, so the risk of significant infusion reactions is considered to be low. For participants who have an infusion reaction associated with administration of INCAGN01876, signs and symptoms would usually develop during or shortly after drug infusion

and generally resolve completely within 24 hours of completion of infusion. Infusions reactions should be managed according to the guidelines in [Section 5.8.2](#).

5.6 Concomitant Medications:

1) Following start of study drug, concomitant medications and therapies deemed necessary for the supportive care and safety of the subject are allowed, provided their use is documented in the subject records and on the appropriate case report form. This includes corticosteroids of any dosage for the management of brain edema related to the tumor and/or study drugs. The administration of any other anticancer agents including chemotherapy and biologic agents (such as bevacizumab) is NOT permitted. Similarly, the use of other concurrent investigational drugs is not allowed.

2) List of medications that are prohibited during this study:

- Any anticancer medications, including chemotherapy or biologic therapy other than the study medications
- Any immunological-based treatment for any reason, with the exception of corticosteroids
- Any investigational agents other than INCAGN01876 and INCMGA00012
- Radiation therapy other than the SRS (8Gy x 3 fractions) administered as part of this protocol
 - Live vaccines. Examples include but are not limited to measles, mumps, rubella, varicella/zoster, yellow fever, rabies, Bacillus Celmette-Guerin (BCG), and typhoid. Intranasal influenza vaccines are not allowed.

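### Section 5.8.2 allows an optional half-rate restart with no grade limit, so it covers some grade 3 infusion reactions for which Section 5.7 requires permanent discontinuation

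*Combined protocol and SAP*

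**What the plan says.** **Section 5.7 (Study Drug Discontinuation Criteria).** A grade 3 or higher infusion reaction clearly linked to one study drug means that drug must be stopped permanently; the other may continue. If it is unclear which drug was responsible, both must be stopped permanently. Section 3.3 ends treatment once any 5.7 criterion is met.

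**Section 5.8.2 (Management of infusion-related reactions).** An acute infusion reaction is any adverse event during the infusion or in the two hours after it. "The infusion should be interrupted if any of the following AEs are observed": nine bullets follow, covering cough, rigors or chills, rash or pruritus, urticaria, diaphoresis, hypotension, dyspnea, vomiting and flushing. None carries a grade. Then: "The reaction(s) should be treated symptomatically, and the infusion may be restarted at" 50% of the original rate. Where investigators see a need to treat or stop other than as described, "they should use clinical judgment to provide the appropriate response according to typical clinical practice". Finally, "The infusion should be terminated and NOT restarted if any of the following AEs occur": anaphylaxis, laryngeal or pharyngeal edema or severe bronchospasm, chest pain, and seizure.

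**Section 5.5.1 (INCMGA00012).** "Participants who experience life-threatening infusion reactions should not be retreated with INCMGA00012". Also, "Secondary prophylaxis is recommended for participants who have experienced IRRs to INCMGA00012", with no grade stated.

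**Routing.** Section 1.3.2.3 says "Specific infusion reaction treatment guidelines are provided in" Section 5.8.2. Section 5.5.2 says "Infusions reactions should be managed according to the guidelines in" the same section, and 5.5.1 has the same instruction. None of 5.5.1, 5.5.2 or 5.8.2 mentions 5.7 for infusion reactions.

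**The concern.** Infusion reactions are handled at the chairside, from the section the protocol names for that purpose. That section gives a permission with no upper grade, while the rule that withdraws it at grade 3 sits elsewhere and is not cited. Someone working from 5.8.2 alone could restart an infusion at half rate in a subject whose reaction has already met a mandatory stop. At stake is re-exposure of a few subjects to a drug they should no longer receive. No operating characteristic of the trial is involved.

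**Working it through.** The main check is a comparison of texts; arithmetic is needed only for how often the situation might arise.

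**1. Does the 5.8.2 permission reach grade 3?**

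| Reaction | 5.8.2 | 5.7 |
|---|---|---|
| Grade 1-2, one of the nine signs | Interrupt, treat, may restart at half rate | No infusion-reaction stop |
| Grade 3, one of the nine signs, no event on the do-not-restart list (e.g. hypotension, dyspnea) | Interrupt, treat, may restart at half rate | Permanent stop: one drug, or both if unclear |
| Any event on the do-not-restart list | End this infusion | Permanent stop if grade 3 or higher |

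The second row is the gap. The do-not-restart list is defined by event type, so grade alone never moves a reaction onto it. Section 5.8.2 contains no grade threshold, no permanent-discontinuation rule and no reference to 5.7. Appendix 1 has no infusion-reaction table, so it does not supply one.

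**2. Does 5.5.1 close the gap?** Table 14 (Section 9.1.1) defines grade 3 as severe but short of immediate threat to life, and uses life-threatening wording for grade 4. The 5.5.1 bar therefore does not reach grade 3. It is a true subset of the 5.7 rule: everyone it bars is also barred by 5.7. The prophylaxis sentence is silent on grade. Section 5.5.2 states no re-treatment bar for INCAGN01876.

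**3. Which trial rules are touched?** Section 3.1 counts run-in subjects who experience a 5.7 criterion. The reaction itself meets that criterion, whether or not the infusion was restarted. Evaluability for the primary endpoint (Section 8.2.1) rests on the final dose and schedule, at least one dose of both drugs and at least one SRS fraction. Neither rule depends on 5.8.2.

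**4. How often?** Inputs are from Table 3 (Section 1.3.1.2), INCMGA00012 monotherapy. Intervals are exact (Clopper-Pearson): lower limit = the 0.025 quantile of Beta(x, n − x + 1), upper limit = the 0.975 quantile of Beta(x + 1, n − x). For x = 0 the upper limit is 1 − 0.025^(1/n).

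- Any grade: 1/37 + 3/132 + 0/15 + 1/15 gives (1 + 3 + 0 + 1)/(37 + 132 + 15 + 15) = 5/199 = 2.5% (0.8% to 5.8%). Section 5.5.1 also gives five of 199.
- Most that could be grade 3 or higher: that study made every grade 3 or greater infusion reaction an adverse event of special interest (AESI). One of the five, at 750 mg, is footnoted as not an AESI, so it drops out. 5 − 1 = 4, and 4/199 = 2.0% (0.6% to 5.1%). For 32 subjects, 32 × 4/199 = 0.64.
- Fewest: the same study also made grade 2 or greater immune-related events AESIs. In the 3 mg/kg Q2W column the other rows sum to 3 + 3 + 2 + 2 + 1 + 1 + 1 + 1 + 1 = 15, against 16 subjects with an AESI. If a subject counts at most once per row, at least one infusion reaction was counted as an AESI, but it could have qualified as a grade 2 immune-related event. So the minimum is 0/199, with upper limit 1 − 0.025^(1/199) = 1.8%.
- At this trial's 500 mg Q4W dose: 0/15, upper limit 1 − 0.025^(1/15) = 21.8%.
- INCAGN01876: Tables 4 to 6 list no infusion reactions above their reporting cut-offs, so no rate is available.

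**The case against.** The strongest reply is that nothing here conflicts: 5.7 says must, 5.8.2 says may, and a site can obey both. Section 5.7 is not obscure. It stands directly before 5.8 and is cited in 3.1, 3.1.3, 3.2 and 3.3, and this is a single-center study. The two sections also do different jobs, one on permanent discontinuation and the other on the infusion in progress. Section 5.8.2 carries its own limits, and few clinicians would restart in a patient with a severe reaction. Most of this stands, and it is why the point is minor. It does not remove the point: the permission as worded includes cases that the binding rule forbids, and nothing in 5.8.2 tells the reader that discretion ends at grade 3.

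A second reply is that the grade of a sign need not be the grade of the infusion reaction, and the CTCAE descriptions for infusion reactions are not in the documents. This stands in part, since the plan does not say which CTCAE term is to be graded. But 5.8.2 defines the reaction as any adverse event in the window, so hypotension graded 3 during an infusion is, on the protocol's own definition, a grade 3 reaction.

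Three stronger readings are tempting and not supported:

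- A reader might infer that 5.5.1 licenses re-treatment after grade 3. It does not say that only life-threatening reactions bar re-treatment, and its prophylaxis advice can be read as applying to subjects still eligible under 5.7.
- A reader might infer that the run-in count could be distorted. Section 3.1 counts criteria experienced, so the formal rule is intact.
- A reader might infer from Table 3 that grade 3 reactions have occurred with INCMGA00012. The table is also compatible with none.

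**Conclusion.** The point holds as a minor safety-wording inconsistency. Section 5.8.2 permits, without requiring, a half-rate restart in some grade 3 reactions for which 5.7 demands permanent discontinuation, and the routing sections lead only to 5.8.2. Section 5.7 controls, so a site that applies it breaches nothing. Section 5.5.1 is narrower than 5.7 on re-treatment and silent on grade for prophylaxis; it does not contradict 5.7.

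The size is small and poorly known: 2.5% for reactions of any grade, and 0% to 2.0% (0 to 4 of 199) for grade 3 or higher, which is at most about 0.6 of 32 subjects as a point estimate. These figures assume that monotherapy rates, mostly at other doses and schedules, carry over to this combination. They count reactions, not wrongful restarts, which would also require 5.7 to be overlooked.

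**What to change.** Adopt the grade 3 threshold already in 5.7.

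- **Section 5.8.2:** limit the half-rate restart to grade 1-2 reactions. Add that a grade 3 or higher reaction ends the infusion and triggers the 5.7 rule (one drug if clearly linked, both if unclear). Keep the do-not-restart list and the judgment clause.
- **Section 5.5.1:** change the re-treatment bar from life-threatening reactions to grade 3 or higher, with a pointer to 5.7.

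Sections 1.3.2.3 and 5.5.2 need no separate rule, because they already lead to 5.8.2. The cost is amendment wording only, with no change to sample size, visits or analysis.
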